### **12.3.5. Analysis of Efficacy Variables**

All efficacy variables will be analyzed within the PD population.

Efficacy variables include:

- Proportion of subjects with objectively documented new or progressive symptomatic VTE will be summarized overall and by age groups during dalteparin treatment; the proportions will be accompanied by an exact 95% confidence interval;
- Proportions of subjects with progression, regression, resolution, or no change in the qualifying VTE will be summarized overall and by age groups during dalteparin treatment; the proportions will be accompanied by an exact 95% confidence interval;
- Time to first episode of recurrent VTE will be analyzed using Cox regression model to assess recurrent VTE during dalteparin treatment, with prognostic factors (eg, age group, baseline tumor type). Kaplan Meier estimates of time will also be produced.

Exploratory analyses:

- Logistic regression model assessing if subjects achieve an Anti-Xa therapeutic range during the Dose Adjustment Phase, using the Odds Ratio of prognostic factors of age, gender, chemotherapy status, and dose of dalteparin.

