
Pharmacodynamic Endpoints
	
Pharmacodynamic Evaluation:
 
Primary Endpoints:
 
 
• Determine the median dose of dalteparin (IU/kg) associated with the achievement of the therapeutic anti-Xa level (0.5-1.0 IU/mL) among subjects that achieved their therapeutic anti-Xa level during the dose adjustment phase, for each age cohort group;
 
• Anti-Xa activity versus time profile following dalteparin treatment will be explored using a population PD analysis methodology. Population PD parameters such as clearance, volume of
 

	
distribution, absorption rate constant will be estimated based on anti-Xa levels collected during dose adjustment phase, PD phase and follow-up phase. Age and other relevant covariates will be explored in the population PD analysis.

Efficacy Endpoints (all are secondary):
	
 
• Proportion of subjects achieving an anti Xa therapeutic range of 0.5 to 1.0 IU/mL during the Dose Adjustment Phase;
 
• Proportion of subjects with objectively documented new or progressive symptomatic VTE during dalteparin treatment;
 
• Proportions of subjects with progression, regression, resolution, or no change in the qualifying VTE during dalteparin treatment;
 
• Time to first episode of recurrent VTE during dalteparin treatment.
 

Safety Endpoints (all are secondary):
	
 
• Proportion of subjects with major bleeding during dalteparin treatment;
 
• Proportion of subjects with minor bleeding during dalteparin treatment;
 
• Relationship between major bleeding event and the Anti-Xa level during dalteparin treatment if data permits;
 
• Description of subjects' adverse events (AE) throughout the study period;
 
• Summary of chemistry, hematology, vital signs and physical examinations;
 
• Time to first major bleeding events during dalteparin treatment.
 

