### **12.3.2. Definition of Study Populations for Analysis**

There will be two analysis populations defined in the study.

- Safety Population: Subjects who receive at least one treatment of dalteparin. All safety analysis will be based on this population;
- Pharmacodynamic Population: Subjects in the Safety Population who achieve therapeutic range of anti-Xa during Dose Adjustment Phase. This population will be the primary analysis population for PD and efficacy analysis.

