### **12.3.4. Analysis of Pharmacodynamic Variables**

All PD variables will be analyzed within the PD population.

The primary study analysis will be a PD evaluation of dalteparin based on Anti-Xa levels using a population PD analysis methodology. Due to the sparse plasma sampling strategy, population PD analyses will be explored. The PD effect (Anti-Xa level) is used as a surrogate PK of dalteparin for the time course of drug exposure. The population PD analysis may also be named as a population PK analysis. Details of the Population PD analysis will be described in a separate population PD modeling analysis plan document and results will be presented in a separate population PD report.

The secondary PD analyses will include the proportion of children achieving an Anti-Xa therapeutic range of 0.5 to 1.0 IU/mL at 4 hours  $\pm$  1 hour post-dose during the Dose Adjustment Phase (up to 7 days) and the proportion of subjects who remain within therapeutic range over the Follow-Up Phase (Visits 5, 6 and 7). These analyses will be descriptively summarized for all subjects and by age groups.

The final dose of dalteparin given to a subject during the Dose Adjustment Phase of the study will be considered the maintenance therapeutic dose (ie, the dose achieving an Anti-Xa level of 0.5 to 1.0 IU/mL at 4 hours  $\pm$  1 hour post-dose). The time to achieve the target range is defined as the number of days from the first dose to the final dose that achieves the target Anti-Xa level. The maintenance dose, time to achieve the target range, and number of dose adjustments during the Dose Adjustment Phase will be summarized by age group using summary statistics.

Aggregate PD profiles (curves of Anti-Xa level versus hours after dosing time) and summary measures will be calculated using combined data for all subjects within a given age group.

Additionally, for each age group, the percentage of Anti-Xa levels measured 4 hours post-dose  $\pm$  1 hour post-dose that are outside the target range will be calculated during the Follow-up Phase of the study.

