### **4.1. PD Analysis Set**

The PD analysis set (PD population) will include all subjects who receive at least one dose of study drug and achieve therapeutic range of anti-Xa during dose adjustment phase.

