#### **6.1.1.2. Secondary PD Endpoints**

- Proportion of subjects achieving an anti-Xa therapeutic range of 0.5 to 1.0 IU/mL during the Dose Adjustment Phase.

The count and proportion will be summarized overall and by each age group within the safety population, along with the two-sided exact 95% CI.

- Proportion of subjects who remain within therapeutic range at each visit during the follow up phase (Visit 5, Visit 6 and Visit 7).

The count and proportion will be summarized overall and by each age group, along with the two-sided exact 95% CI.

- The percentage of anti-Xa levels measured 4 hours post dose  $\pm 1$  hour that are outside the target range will be calculated at each visit during the follow up phase of study (Visit 5, Visit 6 and Visit 7).

The count and percentage will be summarized overall and by each age group, along with the two-sided exact 95% CI.

- The maintenance dose, time to achieve the target range, and number of dose adjustment during dose adjustment phase.

The maintenance dose, time to achieve the target range, and number of dose adjustments will be summarized overall and by each age group.

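### The protocol's exploratory logistic model of reaching the anti-Xa range falls under a population made up only of children who reached it, and the SAP omits the model without saying it was dropped

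*Protocol*

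**What the plan says.** **The model.** Protocol Section 12.3.5, under its exploratory analyses, plans a "Logistic regression model assessing if subjects achieve an Anti-Xa therapeutic range during the Dose Adjustment Phase". Four covariates are named: the child's age and gender, whether the child is on chemotherapy, and the dalteparin dose. The synopsis describes the same model under its efficacy analysis.

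**The population.** Section 12.3.5 opens with the rule "All efficacy variables will be analyzed within the PD population". The exploratory item names no other population. Section 12.3.4 has a parallel rule: "All PD variables will be analyzed within the PD population".

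**What that population is.** Protocol Section 12.3.2 defines it as "Subjects in the Safety Population who achieve therapeutic range of anti-Xa during Dose Adjustment Phase". SAP Section 4.1 has the same condition: a subject must have received a dose and must "achieve therapeutic range of anti-Xa during dose adjustment phase".

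**What the SAP does with the outcome.** SAP Section 6.1.1 applies the PD population to PD endpoints unless noted otherwise. Section 6.1.1.2 then notes an exception: the count and proportion achieving range are "summarized overall and by each age group within the safety population, along with the two-sided exact 95% CI". The SAP contains two logistic regressions, one for new or progressive VTE (Section 6.1.2.1) and one for major bleeding (Section 6.3.1). It has none for achieving the range, and its version history does not mention removing one.

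**The concern.** A logistic regression needs both outcomes in the data. Here, the condition for entering the analysis set is the same event as the outcome, so the set has no child with a No. Children who do not reach range in the Dose Adjustment Phase are withdrawn (Protocol Sections 7 and 8.2). They are present in the Safety Population and absent from the PD population.

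At stake is the only planned multivariable analysis of who reaches range. It is unworkable in the protocol and absent from the SAP. If the team changes the population at analysis time, that choice will be unplanned, and the meaning of the dose covariate will still be open.

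**Working it through.** The documents give no expected achievement rate, effect size or power for this model, so there is no stated figure to reproduce. The main result follows from the definitions alone.

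**Step 1. Outcome against population.** Let y = 1 if a child reaches range in the Dose Adjustment Phase.
- Outcome of the model: y (Protocol 12.3.5).
- Membership of the PD population: treated and y = 1 (Protocol 12.3.2; SAP 4.1).
- Therefore y = 1 for every child in the model, whatever the sample size.

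Classing the outcome as a PD variable changes nothing, because Section 12.3.4 applies the same population.

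**Step 2. What the fit would do.** With y = 1 throughout, the log-likelihood is the negative sum of ln(1 + exp(−linear predictor)). It is below 0 for any finite coefficients and rises towards 0 as the intercept grows. For 50 children (the enrolment target) and an intercept-only model, it is −50·ln(1 + e^−b):

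| Intercept b | Log-likelihood |
|---|---|
| 2 | −6.35 |
| 5 | −0.34 |
| 10 | −0.0023 |
| 20 | −0.0000001 |

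There is no finite maximum. As a numerical check, a maximum-likelihood fit with 50 outcomes all equal to 1 and four simulated covariates had not converged after 200 iterations. Its standard errors were about 2 million to 52 million. A penalised fit would return finite values, but these would come from the penalty and not from any contrast between achievers and non-achievers.

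**Step 3. The simple proportion under Protocol 12.3.4.** In the PD population it is 50/50 = 100% by construction. The exact 95% interval has lower limit 0.025^(1/50) = 0.929, so it would print as 92.9% to 100%. That interval says nothing about the achievement rate among treated children.

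**Step 4. The dose covariate.** The protocol does not say which dose is meant.
- *Starting dose.* Protocol Section 5.2 fixes it by age cohort: 125, 150, 125, 125 and 100 IU/kg from youngest to oldest. If age enters as five cohorts, then starting dose = 125 + 25 × (second cohort) − 25 × (fifth cohort), where each bracket is 1 for that cohort and 0 otherwise. It is an exact combination of the age terms and adds nothing. If age enters as a continuous variable, dose is a step function of age and is not perfectly collinear with it.
- *Titrated dose.* Under Sections 7 and 8.2 the dose is changed because a measured level was out of range. It is therefore partly a result of the outcome process.

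**Step 5. After moving to the Safety Population.** Assume 50 achievers and an achievement rate p, with p a range of assumptions. Treated N = 50/p rounded up, and non-achievers = N − 50. The last column uses three one-degree-of-freedom terms (age, gender, chemotherapy status).

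| Assumed p | Treated N | Non-achievers | Non-achievers per term |
|---|---|---|---|
| 80% | 63 | 13 | 13/3 = 4.3 |
| 85% | 59 | 9 | 9/3 = 3.0 |
| 90% | 56 | 6 | 6/3 = 2.0 |
| 95% | 53 | 3 | 3/3 = 1.0 |
| 98% | 52 | 2 | 2/3 = 0.7 |

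The model becomes defined once there is at least one non-achiever, but it is sparse throughout this range.

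**The case against.** **The population is inferred.** The exploratory item names no population and stands after the list of efficacy variables. Section 12.3.2 calls the PD population the primary one for PD and efficacy, which leaves room for another. This weakens the point but does not remove it. The synopsis lists "Proportion of subjects achieving an anti Xa therapeutic range of 0.5 to 1.0 IU/mL during the Dose Adjustment Phase" among the efficacy endpoints and describes the model under efficacy analysis. The PD-variable rule leads to the same set, and nothing in either document assigns the model to the Safety Population.

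**The SAP has dealt with it.** In part this stands. An analyst working from the SAP alone would not run the model, and the proportion is already in the right population there. A reader might infer that the SAP repeats the faulty model; it does not. What remains is a protocol analysis that is neither corrected nor withdrawn.

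**No information on non-achievers is lost.** A reader might infer that this model is the only planned look at which children fail to reach range. The documents do not support that. SAP Section 6.1.1.2 gives the proportion by age group in the safety population, and Section 6.2.2 reports reasons for withdrawal. Only the multivariable analysis is missing.

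**The dose criticism is conditional.** A reader might infer that the dose odds ratio is bound to be reverse-causal. That holds only if the titrated dose is meant, and full redundancy holds only for starting dose with age entered as cohort. The supportable point is that the covariate is undefined and that neither reading gives a clean prognostic factor.

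**The failure would be obvious.** This stands: a constant outcome produces a visible fitting failure and not a plausible wrong result. It is a reason to treat the point as minor.

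**Conclusion.** The point holds, and it is minor. As the protocol is written, the outcome proportion in the model is 100% by definition and no odds ratio is estimable; this rests on no assumed figure. It does rest on reading the section's population rule as covering the exploratory item, which is the only reading the documents provide for. The protocol and SAP also disagree on the population for the descriptive proportion, and the SAP's choice is the informative one.

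The consequence is confined to one exploratory analysis. The primary endpoints, the median dose and the population PD model, do not depend on it. The figure of about 2 to 13 non-achievers depends on assumed achievement rates of 98% to 80% and exactly 50 achievers. The actual numbers could differ, since the enrolment target counts children with viable PD profiles.

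**What to change.** In Protocol Section 12.3.5, the synopsis and the SAP, do one of the following:

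1. **Keep the model.** State that it is fitted in the Safety Population with baseline covariates only: age, gender and chemotherapy status. Leave out the titrated dose; starting dose is redundant if age enters as cohort. Specify a penalised (Firth) fit if non-achievers are few.
2. **Withdraw the model.** State in the SAP that the protocol's exploratory logistic regression will not be performed, and why.

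In either case, amend Protocol Section 12.3.4 so that the proportion achieving range uses the Safety Population, as SAP Section 6.1.1.2 already does.

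The cost is about one sentence in each place, with no new data and no change to sample size. The downside of keeping the model is imprecision: at the counts above, a penalised fit gives finite estimates but wide intervals. Withdrawal is a reasonable choice if few non-achievers are expected, since the SAP's proportions by age group would remain.

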### **12.3.6. Analysis of Safety Variables**

All safety variables will be summarized within the safety population.

Safety analysis will focus on bleeding, AEs, laboratory tests, physical exam, vital signs, treatment exposure, study drug compliance, and subject disposition during dalteparin treatment.

The investigators' assessments for bleeding events will be collected and used as secondary analyses.

1. The safety analysis will include the following:

- Proportion of subjects with any major bleeding events will be summarized overall and by age group during dalteparin treatment; the proportion will be accompanied by an exact 95% confidence interval;
- Proportion of subjects with any bleeding events (major and minor) will be summarized overall and by age group during dalteparin treatment; the proportion will be accompanied by an exact 95% confidence interval;
- Proportion of subjects with any minor bleeding events will be summarized overall and by age group during dalteparin treatment; the proportion will be accompanied by an exact 95% confidence interval;
- Time to first major bleeding events will be analyzed using Cox Proportional Hazard Regression model to assess the major bleeding events during dalteparin treatment with prognostic factors (eg, age group, baseline tumor type, baseline chemotherapy status) in the model. Kaplan Meier estimates of time will also be produced.
- Relationship between major bleeding event and the Anti-Xa level during dalteparin treatment will be analyzed using logistic regression for major bleeding event assessed on prognostic factors (eg, baseline Anti-Xa level [observed at the end of dose adjustment], age).

2. AE and SAEs will be summarized for the number of subjects with treatment-emergent AEs by System Organ Class and Preferred Term (MedDRA coded) overall, by Severity (NCI CTC version 3.0), by Relationship to study drug, by Seriousness, by if leading to dose change and by if leading to subject's discontinuation of the study.
3. Subject disposition, PE, Vital Signs and Labs will be descriptively summarized. Change from baseline for continuous variable will be analyzed using paired-T test.
4. Treatment Exposure: Treatment duration, summary of daily dose, number of subjects with any dose change and number of changes per each subject, frequency of missed or interrupted study drug and the duration per each interruption or missed, and reasons for study drug interruption or missed will be descriptively summarized.
5. Study Compliance:
  - Study Compliance is defined based on the number of daily doses of study medication administered divided by the intended days of treatment;
  - $\geq 80\%$  in this variable will indicate that the subject was compliant. The proportion of subjects that were compliant will be presented.

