	
summarized overall and by age group during dalteparin treatment, as well as monthly. Proportion of subjects with any bleeding and fatal bleeding will also be summarized. Time to the first major bleeding events will be evaluated by the Kaplan-Meier method and the Cox regression model with prognostic factors (eg, baseline anti-Xa level, age group, baseline tumor type, and chemotherapy status in the model. All other AEs will be described. All laboratory data will be summarized as well as vital signs and physical examinations.

--	---

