### **6.3.2. Subject Replacement Policy**

All subjects who prematurely discontinue from the study and do not complete the PD Phase will be replaced until 50 subjects have viable PD Phase Anti-Xa data.

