#### ***MAJOR BLEEDING (Composite of the following)***

- a. Fatal bleeding.
- b. Clinically overt bleeding associated with a decrease in Hgb of at least 2 g/dL in 24 hours.
- c. Overt bleeding deemed by the attending physician to be unrelated to the subject's underlying condition and accompanied by blood product administration.
- d. Overt bleeding which is retroperitoneal, intracranial, intraspinal, intraocular, or intra articular.
- e. Overt bleeding deemed by the attending physician to necessitate permanent discontinuation of trial medication.

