#### ***CLINICALLY RELEVANT NON MAJOR BLEEDING***

- Bleeding resulting in any medical or surgical interventions but which did not meet the criteria for major bleeding.

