#### ***MINOR BLEEDING***

- Bleeding that does not meet the criteria for Major or clinically relevant non major bleeding.
- Screening evaluations may be used as the baseline assessments.

Antithrombin levels are to be performed once within 1 week post-diagnosis of VTE and at each study visit when Anti-Xa samples are drawn.

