### **12. STATISTICAL METHODS**

#### **12.1. Determination of Sample Size**

Subjects, with or without a diagnosis of various cancers within 6 months of the Screening Visit and requiring anticoagulation for the treatment and secondary prophylaxis of VTE, will be enrolled into the following five age groups:

- 0 to < 8 Weeks;
- $\geq$  8 Weeks to < 2 Years;
- $\geq$  2 Years to < 8 Years;
- $\geq$  8 Years to < 12 Years;

- $\geq 12$  Years to  $< 19$  Years.

Target enrollment is 50 subjects. A sample size of 50 subjects is sufficient to estimate Anti-Xa clearance and  $V_d$  of dalteparin. Enrollment will continue until 50 subjects have viable PD profiles after treatment doses of dalteparin.

The sample size was determined based on historical data and a population pharmacokinetic (PK)/PD model, evaluation of the effect of sample scheme and sample size per age stratum on the bias and precision of key PK/PD parameters, after evaluation of total N of 10, 20, 30, 40 and 50 (2, 4, 6, 8, 10 per age stratum as available) and evaluation of single and 2-point sample densities and impact of randomization across strata with 100 trial simulations per design examined. In addition, blood sampling density was also considered after the subject sample size was determined. Single-point sampling designs yielded unacceptable bias in total body clearance of the drug (CL) and/or  $V_d$ ; confounding of effects if blocked within stratum. Double sampling at 3, 8 and 5, 12 hours post-dose performs more efficiently. Therefore, randomized two-sample design per each subject was also determined.

See [Appendix 3](#) for additional information regarding the trial simulation strategy.

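### Clinically relevant non-major bleeding is defined as its own class, but no analysis reports it, and a child whose only bleed is of this class is in no SAP bleeding proportion

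*Protocol*

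**What the plan says.** **Definitions.** Protocol 9.1.2 gives three classes. Major bleeding is a composite of five criteria. Clinically relevant non-major (CRNM) bleeding is "Bleeding resulting in any medical or surgical interventions but which did not meet the criteria for major bleeding". Minor bleeding is "Bleeding that does not meet the criteria for Major or clinically relevant non major bleeding". Minor therefore excludes CRNM by its own wording.

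**Planned summaries.** Any bleeding is handled in three ways:

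- The protocol synopsis, under Safety Analysis, does not restrict it by class: "Proportion of subjects with any bleeding and fatal bleeding will also be summarized".
- Protocol 12.3.6 adds a parenthesis: "Proportion of subjects with any bleeding events (major and minor) will be summarized overall and by age group during dalteparin treatment". It also plans separate major and minor proportions.
- SAP 3.4 and 6.3.1 plan a major proportion, a minor proportion, and time-to-event and logistic analyses of major bleeding. They contain no any-bleeding summary.

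CRNM is not named in any objective, endpoint or analysis of either document. The SAP does not restate the bleeding definitions.

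**Denominator.** Protocol 12.3.2 defines the Safety Population: "Subjects who receive at least one treatment of dalteparin. All safety analysis will be based on this population". Under Protocol 6.3.2, subjects who stop early without completing the PD Phase "will be replaced until 50 subjects have viable PD Phase Anti-Xa data", so the Safety Population can exceed 50.

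**The concern.** The plan reports the most serious and the least serious class and leaves out the middle one. It counts bleeds that needed no intervention and omits non-major bleeds that did need one. Protocol 12.3.6 makes bleeding a main focus of the safety analysis, so this gap matters more than a missing row in a routine table would.

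Two things are at stake. First, read literally, the 12.3.6 total is labelled as any bleeding but excludes a class that the protocol itself defines. The error has one direction: it can only lower the proportion. Second, the synopsis and 12.3.6 can give different any-bleeding figures from the same data, and the SAP, which governs the tables, gives none.

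Many bleeds that lead to an intervention are already major, so only the remainder is affected. That remainder is real. One major criterion is "Overt bleeding deemed by the attending physician to be unrelated to the subject's underlying condition and accompanied by blood product administration". An overt bleed treated with blood products but judged related to the underlying condition fails that criterion. If it meets no other major criterion, it is CRNM. The trial enrols children under active cancer treatment, so that judgement can plausibly arise.

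**Working it through.** **Step 1. Map the classes to the planned proportions.** Under 9.1.2 the class depends on two facts: whether a bleed meets a major criterion, and whether it led to a medical or surgical intervention. The entries below are for a child with one bleed.

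| Meets a major criterion | Led to intervention | Class | SAP major | SAP minor | 12.3.6 any bleeding, read literally | Synopsis any bleeding |
|---|---|---|---|---|---|---|
| yes | yes | major | yes | no | yes | yes |
| yes | no | major | yes | no | yes | yes |
| no | yes | CRNM | **no** | **no** | **no** | yes |
| no | no | minor | no | yes | yes | yes |

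Three of the four rows fall in exactly one SAP proportion. The CRNM row falls in none, and only the unrestricted synopsis line counts it.

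**Step 2. Effect per child.** The documents state no bleeding rate, so there is no plan figure to reproduce. Without assuming any rate, each CRNM-only child lowers the 12.3.6 proportion by 1/N:

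- N = 50, the target: 1/50 = 2.0 points.
- N = 60, an assumed Safety Population after replacements: 1/60 = 1.7 points.
- An age group of 10: 1/10 = 10 points. No age-group size is fixed. Ten is the largest stratum in the Protocol 12.1 simulations ("total N of 10, 20, 30, 40 and 50 (2, 4, 6, 8, 10 per age stratum as available").

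With the Clopper-Pearson interval of SAP 5.2.1, one CRNM-only child and no other bleed in an age group of 10 is reported as 0/10 = 0% (0 to 30.8%) instead of 1/10 = 10% (0.3 to 44.5%).

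**Step 3. Illustration for the whole trial.** Assume 1 major-bleed child and 5 minor-only children, and let k be the number of CRNM-only children. The 12.3.6 count is 1 + 5 = 6 whatever k is. The synopsis count is 6 + k.

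| N | k | 12.3.6, read literally | All three classes |
|---|---|---|---|
| 50 | 1 | 6/50 = 12% (4.5 to 24.3%) | 7/50 = 14% (5.8 to 26.7%) |
| 50 | 3 | 6/50 = 12% (4.5 to 24.3%) | 9/50 = 18% (8.6 to 31.4%) |
| 60 | 3 | 6/60 = 10% (3.8 to 20.5%) | 9/60 = 15% (7.1 to 26.6%) |

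The gap is k/N, so it depends wholly on the assumed k.

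**Step 4. What a CRNM row would show.** At N = 50: 0/50 = 0% (0 to 7.1%), 3/50 = 6% (1.3 to 16.5%), 5/50 = 10% (3.3 to 21.8%). Even a zero count would be informative, because it carries an upper limit.

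**The case against.** The strongest reply is that the parenthesis in 12.3.6 is loose wording. The objectives and endpoints speak only of major and minor bleeding, so the author may have meant the pair to cover everything. On that reading the synopsis and 12.3.6 agree and the 12.3.6 total loses nothing. This may be the intent, and the downward bias does depend on the literal reading. But the definition of minor expressly excludes CRNM, and a programmer will follow the definitions. The reading also leaves the SAP gap untouched.

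A second reply is that CRNM bleeds are not lost. They enter the adverse event summaries, and SAP 6.3.2 lists adverse events by subject. That is true. However, the planned tables are by system organ class, preferred term and severity, and severity grade is not the 9.1.2 classification. The SAP does not give the listing columns, so whether a listing would show the bleeding class is unknown. What can be said is that no CRNM count or proportion is promised.

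A third reply concerns weight and cost. The safety endpoints are secondary, SAP 5.1 sets no hypotheses or decision rules, and the major-bleeding analyses stand. The illustrative counts have no source in the documents, and the intervals overlap widely. A protocol change needs an amendment. The documents also do not show that every earlier bleed in this long-running trial was classified under 9.1.2. These points hold: they limit the priority of the point and qualify its cost, but do not remove the contradiction.

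**Conclusion.** The concern holds. CRNM is a defined class with no class-specific summary in either document. The two protocol statements of any bleeding differ, and the SAP has no such total. A child whose only bleed is CRNM is in no SAP bleeding proportion and, on the literal text of 12.3.6, is counted as having no bleed.

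The omission follows from the documents alone and needs no assumption. The understatement in 12.3.6 requires the literal reading, which the definition of minor supports. Its size is 1/N per affected child; any larger figure rests on assumed counts. The point should be corrected but threatens no primary result, since bleeding is a secondary, descriptive endpoint and the major-bleeding analyses are intact.

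**What to change.** - **Protocol 12.3.6 and synopsis:** define any bleeding as at least one major, CRNM or minor bleed, with the same wording in both places.
- **SAP 3.4 and 6.3.1:** add the proportion of subjects with CRNM bleeding and the proportion with any bleeding across all three classes. Report both overall and by age group, with exact 95% confidence intervals, in the safety population. Cite the Protocol 9.1.2 definitions.
- **Optional:** a major-or-CRNM composite and a table of each child's worst bleeding class.

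The cost is one definition in the protocol and two rows in a SAP table. No new class definition is needed, because 9.1.2 already gives investigators one. If a protocol amendment is not wanted for this alone, the SAP rows close most of the gap, and the protocol wording can be aligned at the next amendment. Before the tables are programmed, the sponsor should confirm that the case report form records the class for every bleed; any that were not classified would need retrospective classification.
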